7.9.4.6. Time to Resumption of Prophylactic Treatment

Population	Measurement Period	Analysis Notes
Roctavian Cohort only	All available follow-up data	Definition utilized in this study is relevant to the fields that the DHR collects and will be aligned as best as possible to other definitions utilized external to this study

For participants in the Roctavian Cohort, time to resumption of prophylactic treatment will be measured for participants who received SoC prophylaxis after Roctavian administration during the follow-up period. Treatment utilization patterns in the 3 and 6 months after the resumption of prophylaxis will be described regarding the number of infusions/injections by prophylaxis treatment class, total FVIII dose for participants returning to prophylaxis with FVIII, and frequency of infusions/injections. Summary statistics will be utilized to describe time to resumption including mean, SD, median, IQR, minimum, and maximum.

7.9.5. Other Analyses

Per the resolution requiring the Routine Data Collection and Evaluations for Valoctocogene Roxaparvovec,⁶⁰ additional analyses comparing outcomes between the Roctavian Cohort and classes of SoC prophylaxis (FVIII products and emicizumab), age groups, as well as for the SoC Cohort AAV 5 antibody status will be evaluated (note that PwSHA treated with Roctavian will be AAV5 negative per the indication for use in Europe).

The feasibility of conducting comparative analyses for subgroups will be described during the 18-month interim report, though analyses are planned *a priori*. As the therapeutic treatment strategy for an individual who consents to this study is made independently of the decision to participate in the study, the sample size of specific sub-Cohorts by SoC therapeutic classes is not known. The feasibility of conducting a comparative analysis will be based on the characteristics of the sub-Cohort, which will impact the ability of the PS to address confounding, as well as sample size. Similarly, the use of AAV antibody testing among PwSHA who are not considering gene therapy is not known currently. AAV antibody status is not known to impact clinical outcomes among PwSHA and therefore is not part of routine clinical practice currently. The feasibility of a comparison to AAV 5 negative among those in the SoC Cohort will be evaluated similarly to the SoC therapeutic classes (based on both characteristics and sample size). Feasibility of analyses will also consider the ability to conduct comparisons for all vs specific objectives (e.g., it may be possible to conduct sub-group analyses for the primary objective, but not for secondary objectives due to missing data). It is assumed *a priori* that analyses will be feasible.

Baseline characteristics and all primary and secondary outcomes (as appropriate) will be reported (using the same analytic methods as described above) for the following analyses:

SoC Cohort Prophylaxis Treatment Type Subgroup Analysis

- Participants within the SoC Cohort will be stratified based on the prophylaxis treatment received at study consent: emicizumab (alone or in combination with another prophylaxis product), SHL products, EHL products, or PD products. See Table 4 for products that fall within each product type.
- Note, the treatment a participant receives at study consent will only be captured in this analysis, any treatment switch after consent will not be captured by this analysis.
- Each prophylaxis-specific subgroup will be described and compared to the Roctavian Cohort separately as sample size permits.

- A likelihood ratio test will be applied to examine if the SoC treatment types are statistically significantly different.

Age Group Subgroup Analysis

- Participants in both Roctavian and SoC Cohorts will be stratified on age at index date in the following groupings: 18-40, 41-64, 65+.
- A likelihood ratio test will be applied to examine if age groups are statistically significant different across the primary and secondary objective results.

AAV5 Antibody Status Subgroup Analysis

- The study results will be stratified by participants with known AAV5 antibody status at study consent (presence) versus those with no known AAV5 antibody status (absence).
- Missing AAV5 status will be categorized as absence. See Table 3 for operationalization of the AAV5 variable.
- Note, the ability to conduct this subgroup analysis is dependent upon the availability of the AAV5 testing in clinical practice among the SOC cohort.

SoC Switching Sensitivity Analysis

- The study results will be reported for participants in the SoC Cohort who receive Roctavian during the follow-up period and are censored at the time of switching.

Traumatic Bleeds Sensitivity Analysis

If >10% of the population experiences traumatic bleeds as indicated in the DHR (occasion = “traumatic hemorrhage”), a sensitivity analysis will be conducted to compare the ABRs of those with traumatic bleeds as compared to the overall Cohorts (occasion = “spontaneous hemorrhage”).

Switching Sensitivity Analyses

If >15% of the SoC Cohort switches classes of treatment (SHL, EHL, PD, emicizumab) during the follow-up period or if a specific class switching pattern occurs in >10% of the population, a sensitivity analysis will be conducted of participants who remain on the same class for the duration of the follow-up period. ABRs will be calculated for this population that do not switch FVIII classes to understand how this differs from the ABRs for the overall SoC Cohort.

COA measures (as described in Section 7.9.4.4) will be described for participants in the SoC Cohort who stay on the same class of treatment throughout the duration of the follow-up period.

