7.8.3.1. Inverse Probability of Treatment Weighting

IPTW will be implemented to create a baseline reference of propensity score weights for comparison. Using this approach, each participant is assigned a weight representing the inverse probability of being assigned to their respective group. Thus, IPTW aims at giving more importance (i.e., more “weight”) to those participants that have unexpected propensity score values. For the treated group

(Roctavian Cohort), the weight, W , assigned in the IPTW method for each individual, i , based on propensity score, P_i , is:

$$W_i = \frac{1}{P_i}$$

For the control group (SoC Cohort), participants receive weights of:

$$W_i = \frac{1}{(1 - P_i)}$$

As the characteristics of the population that will be treated with Roctavian are unknown at the time of the SAP being drafted, it is possible that large differences in characteristics between the Roctavian and SoC Cohorts will exist. If this is the case, some participants may have extreme propensity score weights and, though representing a small portion of the observed population, have a disproportionate influence on the analysis. This outsized influence of individuals with extreme weights may increase variance and confidence intervals of the ATE estimate.³⁸

Stabilized weights can be used instead of the original, unstabilized weights. To calculate the stabilized weights, the numerator of the unstabilized weights is replaced by the marginal probability of receiving Roctavian and SoC in the overall sample. Additionally, weight values greater than five will be truncated to five due to the potential bias of outliers.^{39, 40}

For the Roctavian Cohort, the stabilized weight, W , assigned in the IPTW method for each individual i , is obtained by dividing the marginal probability of receiving Roctavian (i.e., a propensity score without considering covariates) P_T by individual's propensity score, P_i :

$$W_i = \frac{P_T}{P_i}$$

For the SoC Cohort, participants receive weights of:

$$W_i = \frac{(1 - P_T)}{(1 - P_i)}$$

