7.9. Statistical Analysis Approaches

Descriptive statistics will be generated for all study measures. Descriptive statistics will include means, 95% CIs, SDs, medians, interquartile range (IQR), and minimum and maximum values for continuous variables and frequencies and percentages for the categorical variables. Univariate statistics will be calculated for each measure of interest. Baseline and outcome variables will be compared between the Roctavian and SoC Cohorts using chi-square tests for categorical variables, two-sided t-tests for continuous variables, and Wilcoxon rank-sum tests for medians of continuous variables if the continuous variables are not normally distributed.

For event-based outcomes including the bleeding outcomes, negative binomial models will be fit. Zero-inflated negative binomial models will also be considered if the outcomes show excess zeros (see Section 7.9.3 for details). For binary outcomes, logistic regressions will be fit. For continuous outcomes, general linear regression will be used, with appropriate transformation if needed to ensure model assumptions are met. For COAs, general linear mixed models to account for repeated measures are planned. All the models will be adjusted with propensity score weights and results will be reported based on observed values (before IPTW is applied) and the weighted values (after IPTW is applied).

To adjust for confounding, propensity scores will be calculated and applied using appropriate propensity score IPTW to ensure balance of covariates between the Roctavian and SoC Cohorts. Both unadjusted and propensity score adjusted results will be reported. IPTW is the primary propensity score method for adjustment of confounding. PSM will be performed as an *a priori* sensitivity analysis. Additional details on propensity score methodology is presented in Section 7.8. If additional covariate adjustment is required to balance the Cohorts, multivariable models will be reported.

P-values and SMDs will be reported for comparisons between Roctavian and SoC Cohorts. A p-value <0.05 will be considered statistically significant. All analyses will be based on observed, not projected, data. The sample size calculations are powered for the primary outcome (i.e., ABR), therefore, all p-values associated with secondary outcomes are nominal.

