7.9.3. Analysis of Primary Outcome

Population	Measurement Period	Analysis Notes
All participants For interim and analyses at fixed timepoints, only those with specified amounts of follow-up will be included	≥1 year of follow-up, ≥2 years of follow-up, ≥3 years of follow-up, all available follow-up	Participants with no bleeds will be included as having an ABR of 0

The primary objective to compare the ABR for treated bleeds between the Roctavian and SoC Cohorts will be measured by annualizing the number of bleeds reported in the DHR. Follow-up for ABR will begin as of the index date for the SoC and Roctavian Cohorts. Bleeds will be identified if participants have an “occasion” for treatment of spontaneous bleeding/hemorrhage (regardless of severity). Participants may have multiple bleeds during the reporting period. To calculate ABR, a count of the number of bleeds for each participant will be divided by the number of days in the relevant time period for each participant, multiplied by 365.25. The mean of the individual ABRs for each Cohort will be calculated and then compared between Cohorts over the full follow-up time, as well as during annual increments during the follow-up. For analyses of annual increments, only those participants with full follow-up for that timepoint will be included. For example, analyses comparing ABRs during the first year will only include participants with ≥1 year of follow-up after the index date or analyses comparing ABRs through two years of follow-up will only include participants with ≥2 year of follow-up after the index date. Sample sizes are expected to be reduced in analyses of annual increments for interim analyses as data collection will be ongoing.

Mean, SD, median, IQR, minimum and maximum will be reported for the primary outcome by study group. Histograms will be plotted for the primary outcome by study group. SMD will be calculated to compare Roctavian and SoC Cohort. The participant number in the two Cohorts will be weighted using IPTW generated from the propensity score model. Both unadjusted and propensity score adjusted results will be reported and compared.

Given treated bleeds are event based, a IPTW weighted negative binomial model will be fit to compare ABR between Roctavian and SoC Cohort, with negative binomial distribution and log link function, and the log transformed follow-up time as the offset variable. IPTW will be applied to create

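### The age-subgroup likelihood ratio test names no treatment-by-age term and, if run on the IPTW-weighted models, cannot be referred to chi-square

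*Protocol*

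**What the plan says.** SAP section 7.9.5 forms three age groups in both cohorts ("stratified on age at index date in the following groupings: 18-40, 41-64, 65" and older) and gives one inferential rule for them: "A likelihood ratio test will be applied to examine if age groups are statistically significant different across the primary and secondary objective results". It does not state which models are compared, which term is tested or what reference distribution applies. Protocol section 10.3.8 lists age groups as an additional analysis and gives no test.

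The model has to be inferred from three other statements:

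- SAP 7.9.5 reports the subgroup results "using the same analytic methods as described above".
- SAP 7.9 states: "All the models will be adjusted with propensity score weights".
- SAP 7.9.3 specifies for the primary outcome that "a IPTW weighted negative binomial model will be fit to compare ABR between Roctavian and SoC Cohort".

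On the weights, Protocol section 10.3.5 gives only the unstabilized forms, 1/P and 1/(1-P). SAP 7.8.3.1 repeats them and adds: "Stabilized weights can be used instead of the original, unstabilized weights". It then truncates weights above five, without saying whether this applies to both kinds. SAP 7.9 sets p < 0.05 as the criterion for significance and calls p-values for secondary outcomes nominal.

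**The concern.** A subgroup analysis of a comparative study should ask whether the Roctavian/SoC ratio differs between age groups. The sentence asks whether age groups differ. If older men bleed more in both cohorts and the ratio is constant, a test of age groups is rightly significant, yet the report could present that as an effect that depends on age. The SAP does name interactions elsewhere: treatment by time for the clinical outcome assessments (7.9.4.4) and interaction terms in the propensity model (7.8.2.3). Their absence here therefore leaves real doubt about what is meant.

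If an interaction is meant, a second problem follows. An IPTW-weighted likelihood is not the likelihood of the data. Weights above one make the model act as if it had more participants than were enrolled, and the likelihood ratio statistic grows accordingly. The age analysis is made under the G-BA resolution, so a spurious age difference would go into a report to that body.

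**Working it through.** **1. The plan's own figure.** SAP 7.6 supplies rates 3 (SoC) and 0.85 (Roctavian), dispersion 1.5, one year of exposure, ratio 0.2, null ratio 0.5, one-sided 2.5% and 80% power.

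- V1 = 1/3 + 1/(0.2 × 0.85) + 1.2 × 1.5/0.2 = 15.216
- V0 = (1 + 0.5 × 0.2)² / [0.5 × 0.2 × (3 + 0.2 × 0.85)] + 9 = 12.817
- N1 = (1.960 × √12.817 + 0.842 × √15.216)² / [ln 0.5 − ln(0.85/3)]² = 106.09 / 0.568² = 328.8

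This rounds up to 329 SoC and 66 Roctavian, 395 in total against the stated 397 (330 and 67). The figure reproduces closely and supplies the inputs below.

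**2. What the weights do.** With no confounding, P is about 67/397 = 0.169. The 1/P weight is then 397/67 = 5.9 per Roctavian participant, and the SoC weight is 397/330 = 1.2. Capped at 5, the 67 Roctavian participants count as 67 × 5 = 335. Stabilized weights average about 1, so they do not inflate the sample.

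**3. Approximate error rate for the interaction test.** Assume the same age mix in both cohorts and no confounding. Per-person variances of the log rate at one year are 1/0.85 + 1.5 = 2.676 (Roctavian) and 1/3 + 1.5 = 1.833 (SoC).

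- True variance of the log rate ratio: 2.676/67 + 1.833/330 = 0.0455
- Variance the capped weighted model believes: 2.676/335 + 1.833/397 = 0.0126
- Inflation of the statistic: 0.0455/0.0126 = 3.6

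Three age groups give 2 df, with a 5% critical value of 5.991. The chance of exceeding it is exp[−5.991/(2 × 3.6)] = 44%. Without the cap, the believed variance is (2.676 + 1.833)/397 = 0.0114, the inflation is 4.0 and the rate is 47%.

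**4. Simulations with the same rate ratio at every age.** The first used 397 participants with 17% treated, age mean 42-48 and SD 14 (assumed), and 129-219 usable studies per setting. The second used 400 participants with about 70 on Roctavian, an assumed age mix of 50/38/12%, none to strong confounding, and about 800 runs per setting. Both used 1 or 3 years of exposure.

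| Treatment-by-age test, nominal 5% | First | Second |
|---|---|---|
| LRT, 1/P weights, uncapped | 54-62% | 47-62% |
| LRT, 1/P weights capped at 5 | not run | 35-47% |
| LRT, stabilized weights capped at 5 | 9-17% | 7-13% |
| LRT, unweighted | 4-8% (covariate-adjusted) | 5-8% |
| Robust (sandwich) Wald | 27-31% | 10-15% |

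A third simulation gave about 45% (1/P capped), 55% (1/P uncapped), 7% (stabilized, capped) and 4% (unweighted, covariate-adjusted). The Wald excess comes from the Roctavian group aged 65 or older, which held about 3 people in the first simulation and about 8 in the second.

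**5. Literal reading.** In the second simulation the test of age groups, with stabilized weights, was significant in 5-9% of studies when age had no effect on bleeding. With assumed rates 22% and 49% higher in the two older groups of both cohorts it was significant in 41-48%.

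**The case against.** The strongest reply is that the sentence was meant as a heterogeneity test. The objectives are Roctavian-versus-SoC comparisons, so a difference across their results may mean a difference in those comparisons. This is a fair reading, and it makes the wording ambiguous rather than plainly a main-effect test. It does not supply a tested term or a valid reference distribution.

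The second reply is that stabilized weights are intended. A cap at five makes little sense for 1/P weights that average 5.9 in the Roctavian Cohort. SAP 7.8.3 names stabilization as the way to reduce extreme weights, and 7.8.3.1 trims only if extremes remain after it. This also has force: on that reading the inflation is modest, 7-17%. But the text leaves stabilization optional.

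The weighted fit is indeed inferred, since the SAP also reports unadjusted results and the age sentence does not say which fit carries the test. Secondary p-values are nominal and subgroup comparisons are subject to a feasibility review, which limits the consequences.

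Four stronger readings are tempting, and the documents do not support them:

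- The 41-48% in step 5 is not an error rate. Under that assumption age groups really do differ, and the test correctly says so.
- The uncapped 47-62% is not the plan's operating characteristic if the cap applies to all weights.
- Outcomes compared by t-test, such as FVIII per kg, do not lack a likelihood. SAP 7.9 plans general linear regression for continuous outcomes.
- The parallel sentence on SoC classes ("A likelihood ratio test will be applied to examine if the SoC treatment types are statistically significantly different") was not examined numerically, so nothing is claimed about it here.

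**Conclusion.** The point holds in limited form. The SAP fixes a test but not the hypothesis that an age-subgroup analysis needs. On the literal reading, a significant result carries no information about effect modification. On the interaction reading, with the weighted models the SAP implies, the chi-square reference is wrong. About 35-47% of null studies reject with capped unstabilized weights, and about 7-17% with capped stabilized weights.

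The first range agrees with the hand calculation of 44%, which uses only the plan's own inputs, equal age mixes and no confounding. The simulated ranges also depend on the assumed age mix, age effects and strength of confounding. A reader might infer that false claims of age dependence would be common however the plan is carried out. That does not follow, because with stabilized weights the excess is small. This is a correction of wording and inference that should be made before the SAP is final, and it does not affect the primary comparison.

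**What to change.** Replace the sentence with wording such as: *Effect modification by age is assessed by the treatment-by-age-group term. A likelihood ratio from a weighted model is not referred to the chi-square distribution.* Then fix one method of inference:

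- a likelihood ratio test in an unweighted model that carries the propensity-score covariates as regressors (4-8% rejection in simulation); or
- the weighted model with stabilized weights, with a bootstrap that re-estimates the propensity score in each resample. This option was not simulated here.

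Report the Roctavian/SoC estimate with its confidence interval in each age group. Set in advance a minimum number of Roctavian participants per age group, below which adjacent groups are merged. A robust Wald test alone is not enough, since it rejected in 10-31% of null studies when the oldest Roctavian group was very small.

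The cost is a few sentences and some extra model fits. The drawback of the unweighted option is that it tests a covariate-conditional interaction, which need not match the weighted average treatment effects reported per age group. The bootstrap keeps the weighted effect at the price of more computation.

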10.3.8. Other Analyses

Per the resolution requiring the Routine Data Collection and Evaluations for Valoctocogene Roxaparvovec ([AM-RL 2023](#)), additional analyses comparing outcomes between the Roctavian Cohort and classes of SoC prophylaxis (eg, SHL FVIII, EHL FVIII, PD FVIII, and emicizumab), age groups, as well as for the SoC Cohort that is AAV 5 antibody negative will be evaluated. (Note that PwSHA treated with Roctavian will be AAV5 negative per the indication for use in Europe.)

The feasibility of conducting comparative analyses for subgroups will be described during the 18-month interim report, though analyses are planned *a priori*. As the therapeutic treatment strategy for an individual who consents to this study is made independently of the decision to participate in the study, the sample size of specific sub-cohorts by SoC therapeutic classes is not known. The feasibility of conducting a comparative analysis will be based on the characteristics of the sub-cohort, which will impact the ability of the PS to address confounding, as well as sample size. Similarly, the use of AAV antibody testing among PwSHA who are not considering gene therapy is not known currently. AAV antibody status is not known to impact clinical outcomes among PwHA and therefore is not part of routine clinical practice currently. The feasibility of a comparison to AAV 5 negative among those in the SoC Cohort will be evaluated similarly to the SoC therapeutic classes (based on both characteristics and sample size). Feasibility of analyses will also consider the ability to conduct comparisons for all vs specific objectives (eg, it may be possible to conduct subgroup analyses for the primary objective, but not for secondary objectives due to missing data). It is assumed *a priori* that analyses will be feasible.

In addition to the evaluation of the pre-specified sub-group analysis regarding SoC therapeutic classes and AAV 5 antibody status, other sub-group analyses may be considered based on the observed characteristics of the cohorts that consent into the AbD. As the characteristics of the PwSHA in Germany who will receive Roctavian are not known, nor the characteristics of those on SoC therapies who will consent into the AbD, any additional analyses will be detailed in the SAP and discussed in the interim reports (described below).

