Variable	Captured in DHR	DHR data field name(s)	Operational definition/description
			
 Presence of known significant hepatic fibrosis or cirrhosis at index is an exclusion criterion, which will be confirmed at time of enrollment based on DHR field confirming that the participant fulfills the AbD inclusion/exclusion criteria.
Other comorbidities	Yes	
 Other diseases 	
 Prespecified list of comorbid diseases including: 
 Malignancy: expected to be defined consistently with the safety outcomes Hypertension is sustained elevation of resting systolic blood pressure (≥ 130 mm Hg), diastolic blood pressure (≥ 80 mm Hg), or both¹⁵ Osteoporosis is a progressive metabolic bone disease that decreases bone mineral density (bone mass per unit volume), with deterioration of bone structure. It is defined as DXA results for T-scores $\leq -2.5$¹⁶
Von Willebrand factor	Yes		
 Measured in IU/mL
Target joints	Yes	
 Localization Bleeding location 	
 Yes/No If localization = "target joint", then target joints will = "yes" Number and location of target joints will be based on location (shoulder, elbow, hip, knee, ankle joint, or other joint) and side (left, right, not applicable, or unknown) of bleeds identified as "target joint" For example, if target joint bleeds are recorded at the same location on both sides (e.g., a target joint bleed at the left ankle and a separate target joint bleed at the right ankle), this will be counted as 2 separate target joints. If the target joint location is "other joint" or the side of bleeding is "not applicable or unknown", the number of target joints identified from the bleed will be counted as 1 target joint.
AAV5 antibody status (ever)	Yes	
 Have you been tested for AAV antibodies? If yes: tested serotype If yes: date If yes: result (positive/negative) 	
 Derived from AAV testing for AAV5 being conducted and result of positive/negative
Prophylaxis type	Yes	
 Preparation/ medicinal product 	
 FVIII only Non-factor products only (e.g., Emicizumab) FVIII and non-factor products See Table 4 for drug classifications

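### The AAV5 subgroup rule in SAP 7.9.5 does not produce the AAV5-negative SoC comparator that the protocol and the SAP's own text name

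*Protocol*

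**What the plan says.** Protocol 10.3.8, citing the resolution behind the data collection, lists among its additional analyses one comparing Roctavian with SoC classes, "as well as for the SoC Cohort that is AAV 5 antibody negative will be evaluated". SAP 7.9.5 opens by referring only to AAV5 antibody status, but its feasibility paragraph states the same target: "The feasibility of a comparison to AAV 5 negative among those in the SoC Cohort will be evaluated".

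The bullets that define the analysis, later in SAP 7.9.5, stratify by "participants with known AAV5 antibody status at study consent (presence) versus those with no known AAV5 antibody status (absence"). The next bullet reads "Missing AAV5 status will be categorized as absence" and refers to Table 3 for how the variable is built. Table 3 (SAP 7.4.1) defines it by test result: "Derived from AAV testing for AAV5 being conducted and result of positive/negative".

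On how many SoC participants will have a result, SAP 7.9.5 says that "the use of AAV antibody testing among PwSHA who are not considering gene therapy is not known currently" and that testing is outside routine care. It also notes that everyone treated with Roctavian will be AAV5 negative under the European indication, and that the subgroup depends on testing being available in the SoC Cohort.

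**The concern.** Four statements about one subgroup do not agree. Two name a negative-only SoC comparator, one defines a positive/negative variable, and the rule to be programmed splits on whether a status is recorded and sends missing values to *absence*. A programmer following the bullets would not produce the analysis that the protocol describes.

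The subgroup has a specific purpose. The indication requires no detectable AAV5 antibodies, but the study's eligibility criteria do not, and AAV5 status is not among the candidate propensity score variables. This is therefore the only planned analysis that restricts the SoC Cohort to people who match the indication on this point. Since testing is not routine in SoC, missing status is likely to be common, and the rule for missing values decides who is in the stratum.

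**Working it through.** **1. Who falls where.** The bullets can be read in two ways.

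| Reading | SoC in *presence* | SoC in *absence* | Roctavian participants |
|---|---|---|---|
| Status known vs not known | tested positive and tested negative together | untested only | *presence* (negative, result recorded at or around administration) |
| Antibodies present vs absent | tested positive | tested negative plus all untested | *absence* |

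No cell contains tested-negative SoC participants alone. On each reading, the stratum without Roctavian participants allows no comparison.

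**2. Inputs for size.** The plan gives no figure for this subgroup. The only plan number used is the SoC target of 330. The formula in SAP 7.6 with its stated inputs gives 328.8, so 329 SoC and 66 Roctavian, against the stated 330 and 67; 330 is taken as it stands. The share of SoC tested (q) and the share positive (s) are not in the documents. Assumed: q = 10-30%, s = 20-50%, with the same s in tested and untested.

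**3. Present/absent reading.** As fractions of the SoC Cohort:
- retained in *absence*: (1 − q) + q(1 − s) = 1 − qs
- documented negatives as a share of *absence*: q(1 − s) / (1 − qs)
- true positives as a share of *absence*: (1 − q)s / (1 − qs)
- number of documented negatives: 330 × q(1 − s)

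| q | s | Retained | Documented negative | Truly positive | Documented negatives, n |
|---|---|---|---|---|---|
| 0.1 | 0.2 | 0.98 | 0.08/0.98 = 8.2% | 0.18/0.98 = 18.4% | 26.4 |
| 0.1 | 0.5 | 0.95 | 0.05/0.95 = 5.3% | 0.45/0.95 = 47.4% | 16.5 |
| 0.3 | 0.2 | 0.94 | 0.24/0.94 = 25.5% | 0.14/0.94 = 14.9% | 79.2 |
| 0.3 | 0.5 | 0.85 | 0.15/0.85 = 17.6% | 0.35/0.85 = 41.2% | 49.5 |

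More testing shrinks the problem without removing it. With s = 20-50%, untested participants are 56-67% of *absence* at 50% tested and 29-40% at 75% tested.

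**4. Known/unknown reading.** Documented negatives are 0% of *absence* at any q. The SoC side of *presence* holds 330q = 33 to 99 people, of whom a share s, 20-50%, are documented positive.

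**The case against.** Three points count against the concern.

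- *AAV5 status may not matter for bleeding.* SAP 7.9.5 says "AAV antibody status is not known to impact clinical outcomes among PwSHA and therefore is not part of routine clinical practice currently". This stands as a limit: the documents give no ground for saying that mixing positives into the comparator biases the bleeding comparison. It does not justify the coding, because the negative-only comparison is planned anyway and the coded strata cannot check the premise.
- *The SAP keeps the comparison and caveats it.* The feasibility paragraph still names AAV5-negative SoC participants. So the SAP contradicts itself; it has not dropped the analysis. But the caveat is about feasibility, and on the present/absent reading coding missing as *absence* keeps the stratum large even with few or no tested negatives. That would hide the shortage that the 18-month feasibility review is meant to find.
- *The set is not useless.* On the present/absent reading, *absence* is the SoC Cohort minus documented positives, a defensible sensitivity set. This stands: on that reading the faults are its label and the lack of a documented-negative set beside it.

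A reader might go further and infer that the subgroup is bound to nearly repeat the full SoC comparison, so that agreement would pass for confirmation in the eligible population. The documents support that only on the present/absent reading. On the known/unknown reading, *absence* has effectively no Roctavian arm, and *presence* sets Roctavian against tested SoC participants only, positives included.

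**Conclusion.** The contradiction is certain from the texts: on neither reading does SAP 7.9.5 yield documented AAV5-negative SoC participants as the comparator. The percentages in step 3 of the working apply only to the present/absent reading and rest on three assumptions: the tested share, the positivity, and equal positivity in the untested. They are illustrative.

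The reach is limited. This is a secondary subgroup analysis subject to feasibility. The primary analysis and the sample size are unaffected. It should be corrected, but it does not threaten the study's main result.

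**What to change.** Replace the two AAV5 bullets in SAP 7.9.5 with the following:

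- Classify SoC participants as documented AAV5 negative, documented AAV5 positive or not tested. Never code missing as negative.
- Compare Roctavian with documented negatives, re-estimating the propensity score in that set if numbers allow.
- Report the number tested. If negatives are too few, or those tested look like a selected group, say so under the existing feasibility provision.
- If wanted, keep the SoC Cohort minus documented positives as a sensitivity analysis under exactly that label.
- Align Protocol 10.3.8, SAP Table 3 and both parts of SAP 7.9.5.

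The cost is some SAP wording and one derived variable. Table 3 already lists whether a test was done, serotype, date and result, so no new data field is needed. The change fits before the SAP is finalised ahead of the 18-month data cut.

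The downside is precision. With the plan's own rates, dispersion and one-year exposure, and no allowance for weighting, power against the 0.5 null with 67 Roctavian participants is about 30-41% if 10% of SoC are tested (16-26 documented negatives) and 51-62% if 25% are tested (41-66), against 80.6% for 330 and 67. A propensity score fitted at the low end would be doubtful, which is why an honest statement that the comparison is not feasible must remain open.
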